9.6.2. Record Retention

To enable evaluations and/or inspections/audits from regulatory authorities or Pfizer, the investigator agrees to keep records, including the identity of all participating patients (sufficient information to link records, eg, CRFs and hospital records), all original signed informed consent documents, copies of all CRFs, safety reporting forms, source documents, detailed records of treatment disposition, and adequate documentation of relevant correspondence (eg, letters, meeting minutes, and telephone call reports). The records should be retained by the investigator according to local regulations or as specified in the clinical study agreement (CSA), whichever is longer. The investigator must ensure that the records continue to be stored securely for so long as they are retained.

If the investigator becomes unable for any reason to continue to retain study records for the required period (eg, retirement, relocation), Pfizer should be prospectively notified. The study records must be transferred to a designee acceptable to Pfizer, such as another investigator, another institution, or to an independent third party arranged by Pfizer.

Study records must be kept for a minimum of 15 years after completion or discontinuation of the study, if required by applicable local regulations.

The investigator must obtain Pfizer's written permission before disposing of any records, even if retention requirements have been met.

9.7. Data Analysis

General Considerations

The analysis plan will be fully described in a written and approved statistical analysis plan (SAP). The SAP will describe all statistical analyses, including definition of study outcomes and scoring of the different scales, and will further provide a detailed description of analyses to be performed and describe methods to deal with missing data and censoring. The final SAP will include the tables shell to be used for the final data analyses. Moreover, an interim analysis(es) to characterize dropouts and collecting only critical data elements (ie, variables aligned with the study objectives) to minimize site/participant burden will be conducted.

Descriptive analyses will be carried out to evaluate the objectives of the study. In order to describe the profile of the patients under study, a descriptive statistical analysis of each and every one of the variables included in the notebook will be carried out for this purpose.

Categorical variables are described by their absolute and relative frequency. Continuous variables are described with total n, valid n, n unavailable, means, standard deviation, quartiles, minimum and maximum. Progression-free survival will be measured from treatment initiation to evidence of tumor progression or death. Overall survival will be measured from treatment initiation to death. Patients will be censored at last control, if are lost during the follow-up.

The safety assessment will be based primarily on the frequency and severity of AE. AE will be summarized by presenting the number and percentage of these figures in the total number of patients. The absolute and variable frequencies of each AE with respect to the total number of reported AEs will also be presented. If applicable, the codification of the Medical Dictionary for Regulatory Activities (MedDRA)) will be useful Medication will be coded using WHO Drug Dictionary.

Survival analysis will be performed using Kaplan Meier method. A Cox regression model will be carried out to find independent variables associated with overall survival or time until disease progression.

Detailed methodology for summary and statistical analyses of data collected in this study will be documented in a statistical analysis plan (SAP), which will be dated, filed, and maintained by the sponsor. The SAP may modify the plans outlined in the protocol; any major modifications of primary endpoint definitions or their analyses would be reflected in a protocol amendment.

9.8. Quality Control

As this is a post-authorisation study, the same procedures will be followed by the investigator as in routine clinical practice.

However, the investigators are responsible for ensuring that the protocol and Good Clinical Practice (GCP) standards are complied with.

Study sites might be subject to face-to-face or remote monitoring by the person appointed by the sponsor and a review by the Independent Ethics Committee (IEC) and/or quality assurance audits conducted by the relevant regulatory authorities and the study sponsor.

9.9. Limitations of the Research Methods

This is a non-interventional study in clinical practice. Study results might not reflect pivotal clinical trial results, in which patients are assigned to active or control group by chance (through randomization) to reduce errors or bias.

Additionally, our study population exhibits a low incidence of NSCLC patients, approximately 3-4%. Consequently, the current study is descriptive in nature, as it lacks the statistical robustness (relatively small sample, but almost similar to the total of patients included in the pivotal trial) necessary to establish a significant association between a specific adverse event and the drug. The medical literature contains analogous examples of post-authorization safety studies that offer valuable information²⁰⁻²² required by physicians and, in our case, considering that lorlatinib has become the first TKI and biomarker targeted therapy providing the longest efficacy (mPFS not reach after 60.2 months of follow-up in its pivotal trial) reported for all the solid tumors to date⁴.

Data collected in this study will reflect clinical practice in Spain. As a result, they may not be generalizable to studies conducted elsewhere, due to differences in clinical practice and patient characteristics.

The study is limited to a data collection and does not generate any risk or benefit to the patient. However, this study will allow progress in the knowledge of the conditions and factors associated with the use of lorlatinib.

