Additionally, our study population exhibits a low incidence of NSCLC patients, approximately 3-4%. Consequently, the current study is descriptive in nature.

Study Population

Patients in 20 Spanish hospitals (clinics, or and primary care centers) must have a confirmed diagnosis of locally advanced and/or metastatic NSCLC with an ALK rearrangement identified by an approved diagnostic test, be older or equal than 18 years and have initiated first-line therapy with lorlatinib at least 7 days and up to 28 days prior to enrolment in the study according to routine clinical practice. They must also sign an informed consent and have a minimum of predetermined data recorded in their medical records. Socio demographic data about the patient's gender, age, height, weight at the treatment initiation will be collected. Additional socio demographic data will be collected: race, along with details regarding their smoking habits, as well as exposure to asbestos and previous personal and family history of cancer, particularly in first-degree relatives. Patients included in clinical trials are also excluded.

Study variables

The following variables will be collected: AE, serious adverse events (SAE), and scenarios involving: exposure during breast feeding, medication error, overdose, misuse, extravasation, lack of efficacy; exposure during pregnancy (EDP), occupational/environmental exposure and treatment-associated mortality as well as time to onset and duration of AEs. Likewise, effectiveness variables as rwPFS rate at 12 and 18 months in the ITT population with and without brain; metastasis at baseline, rwDuration of Response (DoR); rwDuration of Treatment (DoT), rwTime to next therapy/treatment (TTNT)M; rwSystemic and intracranial Objective Response rate (ORR) using Response Evaluation Criteria in Solid Tumors (RECIST v1.1). criteria, rwTime to intracranial progression rate at 12 and 18 months with and without brain metastasis at baseline, rwCumulative incidence of brain metastases (BM) in ITT population at 12 and 18 months (with and without baseline BM), rwOverall survival (OS) rate at 12 and 18m.

Sociodemographic, clinical variables prior to start treatment/on treatment/after treatment with lorlatinib and quality of life data of patients under treatment will be collected.

Data sources

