8. RESEARCH QUESTION AND OBJECTIVES

Research question

 What is the spectrum of adverse events and mitigation strategies associated with lorlatinib as a first line treatment in an ALK+ NSCLC real-world Spanish population?

Primary Objective

• To describe all the spectrum of the adverse events (AEs) of Lorlatinib (CTCAE v6.0) and its mitigation strategies, with special interest in CNS AEs

Secondary Objectives

- To identify factors that are predictive of AEs, with special interest in CNS AEs
- To evaluate the effectiveness of 1L lorlatinib in real-world practice
 - 1. rwPFS rate at 12 and 18 months in the ITT population with and without brain metastasis at baseline.
 - 2. rwDuration of Response (DoR)

- 3. rwDuration of Treatment (DoT)
- 4. rwTime to next therapy/treatment (TTNT)
- 5. rwSystemic and intracranial Objective Response rate (ORR) using Response Evaluation Criteria in Solid Tumors (RECIST v1.1.) criteria
- 6. rwTime to intracranial progression rate at 12 and 18 months with and without brain metastasis at baseline
- 7. rwCumulative incidence of brain metastases (BM) in ITT population at 12 and 18 months (with and without baseline BM)
- 8. rwOverall survival (OS) rate at 12 and 18m
- To evaluate the impact of lorlatinib on patients' quality of life
- To describe ALK testing methods used

Exploratory Objectives (up to 30 patients)

• To identify neuroimaging markers (MRI) that are predictive of the occurrence of CNS AEs

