9. RESEARCH METHODS

9.1. Study Design

This is an observational, non-interventional, prospective, multicenter and nationwide study with the category of PASS (Post Authorization Safety Study), which seeks to answer the research question: what is the spectrum of adverse events and mitigation strategies associated with lorlatinib in a real-world Spanish population? For this purpose, an observational, non-interventional and prospective study design is ideal to faithfully reflect what occurs in the routine clinical practice.

It is important to note that our study population exhibits a low incidence of NSCLC patients, approximately 3-4%. Consequently, the current study is descriptive in nature, as it lacks the statistical robustness (relatively small sample, but almost similar to the total of patients included in the pivotal trial) necessary to establish a significant association between a specific adverse event and the drug.

The primary objective will be to describe all the spectrum of the AEs of Iorlatinib (CTCAE v6.0) and its mitigation strategies with special interest in CNS AEs.

Primary Objective	Corresponding Endpoint			
To describe all the spectrum of the adverse events (AEs) of Lorlatinib (CTCAE v6.0) and its mitigation strategies, with special interest in CNS AEs	Occurrence (number of adverse events) and severity of AEs, with severity determined according to NCI CTCAE v6.0 criteria. Frequency and period of dose reductions as well as concurrent medications used to control AEs will be collected			
Secondary Objectives	Corresponding Endpoints			
To identify factors that are predictive of AEs, with special interest in CNS AEs	To evaluate the relationship of multiple demographic and clinical factors with the incidence of AEs, with special interest in CNS adverse events			
To evaluate the effectiveness of 1L lorlatinib in real-world practice	• Effectiveness will be assessed:			
rwPFS rate at 12 and 18 months in the ITT population with and without brain metastasis at baseline	1. To determine real-world progression-free survival (rwPFS) defined as the time from enrollment to the first occurrence of disease progression (intracranial or systemic) or death from any cause, whichever occurs first, as determined by the investigator using RECIST v1.1. criteria, at 12 and 18 months, in the ITT population with and without brain metastasis at baseline			

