9.2. Setting

The study population includes adult patients aged 18 years or older diagnosed with non-small cell lung cancer who are carriers of the ALK gene rearrangement recruited in an 18-month estimated period from 20 high specialized hospitals at the country level who have started first-line therapy with lorlatinib according to label prescription, with treatment duration of at least 7 days and up to 28 days.

In Spain, molecular diagnosis of ALK rearrangement is routinely performed in patients with non-small cell lung cancer according to the diagnostic guidelines of the Spanish Society of Pathological Anatomy and the Spanish Society of Medical Oncology. Only patients with a confirmed and valid ALK testing will be included in our cohort. Among validated testing methods are the following: FISH fluorescence in situ hybridisation (FISH) Immnunohistochemistry using the D5F3 clon Roche VENTANA (IHC) mainly, PCR polymerase chain reaction (PCR) and the next generation sequencing (NGS)²³.

Given the estimated low incidence rate of 3.4% for this disease among the local population¹⁵, and the difficulty of performing molecular testing in some hospitals at the country level, the

Principal Investigators decided to involve centers specializing in the molecular diagnosis of ALK because otherwise, the lack of expertise in the molecular diagnostics would negatively impact the number of patients that can be enrolled in the study.

Based on data from the CROWN trial, where the incidence of CNS AEs was reported to be 42%, and assuming that the incidence could be higher in real clinical practice but potentially under-detected or recorded as grade 1 cases, they estimated that 116 patients treated with lorlatinib in first-line therapy for ALK+ non-small cell lung cancer are needed. This would provide 80% power to detect an incidence of 55% any grade CNS AEs using a 2-sided test.

Data collection Periods

Patient data will be collected in the following periods:

- **Pre-index period**: since diagnosis to start lorlatinib treatment.
- Index Date: date of start of lorlatinib.
- Post-index period: visits performed under clinical practice since index date and until
 end of study period

Patient data collection will cease at the end of study completion.

Study Visits

The study will be conducted in 5 visits, according to clinical practice:

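### Sites are chosen for ALK diagnostic expertise and the protocol requires neither consecutive invitation nor a count of patients not enrolled, yet Section 9.9 names no selection limitation within Spain

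*Protocol*

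**What the plan says.** On sites, Section 9.2 describes a population "recruited in an 18-month estimated period from 20 high specialized hospitals at the country level". It gives two reasons for the choice of sites: the low incidence of the disease and "the difficulty of performing molecular testing in some hospitals at the country level". For these reasons the "Principal Investigators decided to involve centers specializing in the molecular diagnosis of ALK".

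On scope, Section 9.1 labels the work an "observational, non-interventional, prospective, multicenter and nationwide study" and presents the design as suited to mirroring routine practice. Section 9.9 states "Data collected in this study will reflect clinical practice in Spain", and the sentence after it restricts generalisation only to settings elsewhere. Section 9.9 does not mention how sites or patients within Spain are selected.

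On objectives, the primary one (Section 8) covers the spectrum of adverse events and their mitigation, with emphasis on CNS events. A secondary one is "To describe ALK testing methods used".

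On enrolment, Section 9.2.1 admits adults with ECOG 0-2 who started first-line lorlatinib between 7 and 28 days before entry. Section 9.2.2 excludes trial participants and asks for a documented eligibility check before enrolment. Section 10.1 has each site keep a list of those who took part. Section 11 starts the safety reporting period at the first dose.

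**The concern.** A descriptive safety study stands or falls on who enters it. Two layers of selection operate here, and the limitations section names neither.

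The first is between sites. Hospitals were chosen on a characteristic that Section 9.2 itself says other Spanish hospitals lack, and that characteristic is closely tied to one of the secondary outcomes.

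The second is within sites. The decision to invite is taken one to four weeks into treatment, while adverse events count from the first dose. An investigator may therefore already know about early toxicity when choosing whom to approach. Starters who stop or die before day 7, or who are not approached by day 28, may leave no trace in the study.

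Without a count of those not enrolled, a reader of the final report could not tell whether selection mattered. No later analysis could restore patients who were never recorded, so this has to be settled in the protocol rather than in the SAP.

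**Working it through.** **Side-by-side reading**

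| Point | Protocol text | Consequence |
|---|---|---|
| Site choice | Section 9.2: ALK-expert hospitals, because some others struggle to test | The sample is acknowledged to differ from other Spanish hospitals in diagnostics |
| Claim | Section 9.9: mirrors practice in Spain; caveat only for elsewhere | No limit stated within Spain |
| ALK testing objective | Section 8; method recorded per patient in Section 9.3 | Outcome lies in the domain on which sites were chosen |
| Patient records | Section 9.2.2: eligibility check; Section 10.1: list of participants | Neither counts patients not invited, refusing or out of window |
| Timing | Section 9.2.1: entry on days 7-28; Section 11: events from first dose | Selection that depends on the outcome is possible |

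**The plan's own figure.** Section 9.5 gives 116 patients for 55% against 42%, 80% power, two-sided. Alpha is not stated; I assume 0.05. With the arcsine formula:

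- h = 2·asin(√0.55) − 2·asin(√0.42) = 0.2609
- n = ((1.960 + 0.842)/h)² = 115.3, which rounds up to 116

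The figure reproduces, and this point does not dispute it.

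**Sampling error, for scale.** The 95% half-width at n = 116 is:

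- at 42%: 1.96·√(0.42·0.58/116) = 9.0 points
- at 55%: 1.96·√(0.55·0.45/116) = 9.1 points

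**Illustration of selection.** The documents give no enrolment fraction, so every input here is an assumption. Let r be the probability of enrolment with a CNS event divided by that without. Then observed p = p·r/(p·r + 1 − p).

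- True 42%, r = 0.75: 0.315/0.895 = 35.2%
- True 42%, r = 1.5: 0.630/1.210 = 52.1%
- True 55%, r = 0.75: 0.4125/0.8625 = 47.8%
- True 55%, r = 1.5: 0.825/1.275 = 64.7%

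A second parametrisation is bias = share not enrolled × risk difference between enrolled and not enrolled. With 20-40% not enrolled and a difference of 10-20 points, the bias runs from 0.2·10 = 2 to 0.4·20 = 8 points.

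Under these assumptions the shift ranges from small to about the size of the sampling half-width. The difference sought is 55 − 42 = 13 points. The direction cannot be derived.

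**The case against.** The sentence in Section 9.9 sits under limitations and introduces a caveat, so it is loose wording more than a formal claim of representativeness. Section 9.2 also discloses the site choice openly. Both points are fair. Still, the nationwide label in Section 9.1 points the same way, and the limitations section is where a reader would look for selection within Spain.

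Several stronger readings are tempting, and the documents do not support them:

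- *Enrolment is non-consecutive and unlogged.* The protocol is silent. It does not say so, and it does require a documented eligibility check and a participant list. Only the absence of a requirement can be asserted.
- *Choosing expert sites biases adverse event rates.* Every participant must already have a positive ALK test and be on lorlatinib, so diagnostic capability is not selection on adverse event risk. That specialised centres detect or manage events differently is plausible, since Section 9.5 itself calls CNS events under-detected, but it remains an inference.
- *Site choice largely settles the ALK testing result.* FISH, IHC, PCR and NGS are all accepted and the method is recorded for each patient. The mix remains an open result; it simply describes specialised centres.
- *Clinics and primary care centres take part.* The abstract does read "Patients in 20 Spanish hospitals (clinics, or and primary care centers", but this is a garbled parenthesis. Sections 9.1 and 9.2 consistently describe hospitals. It needs an editorial correction and is no evidence on selection.
- *Frail patients will be passed over.* ECOG 2 is eligible and a legal representative may consent. Nothing shows such exclusion.

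Privacy is a valid objection to a detailed log. With 116/20, or about six patients per site, entries carrying age, sex and disease features for people who never consented could be re-identifiable.

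**Conclusion.** The point holds in a limited form and merits a protocol change. For the ALK testing objective, Sections 9.2 and 9.9 are directly inconsistent: sites were selected on diagnostic expertise that other hospitals are said to lack, so the result describes participating centres and not Spain. For adverse event incidence and mitigation, outcome-aware selection is possible under the protocol as written, because entry follows the first dose by 7 to 28 days and no rule requires inviting or counting everyone.

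Whether such selection will occur, how large it would be and which way it would go cannot be known from the documents. The calculated ranges rest wholly on assumed inputs. They show only that modest selection could matter relative to sampling error. The sample size is unaffected.

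**What to change.** In Section 9.2:

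- Require each site to invite every eligible patient starting first-line lorlatinib during the recruitment window.
- Require a minimal, non-identifying tally of starters not enrolled, as counts by reason: stopped or died before day 7, past day 28, refused, not invited, other.
- State that this flow will be reported with the results.

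In Section 9.9, name site selection and patient selection as limitations and confine conclusions to specialised ALK centres. In Section 8 and wherever the objective is repeated, describe the ALK testing methods as those used in participating centres. Correct the abstract's description of the sites to agree with Section 9.2.

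The tally must run while patients are being recruited (June 2025 to November 2026 in Section 6). The cost is minor site effort, a data-protection check on the tally and a narrower claim. Treatment, endpoints and sample size do not change.

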9.10. Other Aspects

9.10.1. Ethics

This study will be conducted in accordance with the ethical principles that have their origin in the World Medical Association (WMA) Declaration of Helsinki and will be consistent with GCP guidelines and pertinent regulatory requirements.

The study personnel involved in conducting this trial will be qualified by education, training and experience to perform their respective task(s).

The study will be conducted in compliance with the protocol. The protocol, any amendments and the patient informed consent will receive IEC/IRB approval/favorable opinion prior to initiation, according to pertinent regulations.

The decision of the IEC/IRB concerning the conduct of the study will be made in writing to the Investigators, and a copy of this decision will be provided to the Sponsor before the beginning of the study. The Investigator and/or the Sponsor is/are responsible for keeping the IEC/IRB informed of any significant new information about the study.

All protocol amendments will be agreed upon by the Sponsor and the Investigator.

Administrative changes of the protocol are minor corrections and/or clarifications that have no impact on the way the study is to be conducted.

This study follows the Spanish law, Royal Decree 957/2020 of 3rd November 2020, which states the guidelines on observational studies for medicinal products for human use.

